#### **5.13.2.2. Severe Persistent Hyperglycemia**

A summary or listing of initiation of rescue therapy in response to severe, persistent hyperglycemia will be provided by treatment. If there is sufficient number of episodes, time-to-first-event analysis for the initiation of rescue therapy will be conducted by treatment using Cox proportional regression model. A listing of patients initiating rescue therapy will be provided.

#### **5.13.2.3. Pancreatitis**

If data warrants, summaries of adjudicated and investigator-reported pancreatic events will be provided by treatment. Determination of investigator-reported events will be through the predefined Standardized MedDRA Queries (SMQ) search for acute pancreatitis and MedDRA PT of pancreatitis chronic. Detailed searching criteria can be found in [Appendix 1](#). Treatment-emergent adjudication-confirmed pancreatitis will be considered an AESI.

##### **5.13.2.3.1. Pancreatic Enzyme Assessment**

Observed pancreatic enzyme data (p-amylase and lipase) will be summarized by treatment and nominal visit. Additionally, number and proportion of patients with maximum postbaseline pancreatic enzyme value exceeding the following thresholds will be provided by maximum baseline pancreatic enzyme value ( $\leq 1 \times$  Upper Limit of Normal [ULN],  $> 1 \times$  ULN) and treatment:  $\leq 1 \times$  ULN, ( $> 1$  to  $\leq 3$ ) $\times$  ULN, ( $> 3$  to  $\leq 5$ ) $\times$  ULN, ( $> 5$  to  $\leq 10$ ) $\times$  ULN,  $> 10 \times$  ULN.

An MMRM analysis will be used to analyze each pancreatic enzyme with a log transformed (post-baseline measure/baseline measure) response variable, and stratification factors, treatment, nominal visit, and treatment-by-nominal visit interaction as fixed effects, and baseline value as a covariate.

#### **5.13.2.4. Thyroid Malignancies and C-Cell Hyperplasia**

Treatment-emergent thyroid malignancies and C-cell hyperplasia will be identified using a predefined MedDRA HLTs of thyroid neoplasms malignant and PT of thyroid C-cell hyperplasia. Detailed searching criteria can be found in [Appendix 1](#). A summary by treatment and PT and a listing will be provided. Thyroid malignancies and C-cell hyperplasia will be considered as AESI.

#### **5.13.2.5. Malignancies**

The AE database will be searched using pre-defined SMQs to identify events consistent with malignancy. Detailed searching criteria can be found in [Appendix 1](#). A summary by treatment and PT and a listing will be provided. Malignancy will be considered as AESI.

#### 5.13.2.6. Calcitonin

Observed calcitonin data will be summarized by treatment and nominal visit. Additionally, number and proportion of patients with a maximum postbaseline calcitonin value exceeding the following thresholds will be provided by treatment, maximum baseline calcitonin value ( $\leq 20$  ng/L,  $>20$  to  $\leq 35$  ng/L,  $>35$  ng/L),:  $\leq 20$  ng/L,  $>20$  to  $\leq 35$  ng/L,  $>35$  to  $\leq 50$  ng/L,  $>50$  to  $\leq 100$  ng/L,  $>100$  ng/L.

#### 5.13.2.7. Major Adverse Cardiovascular Events (MACE)

Major adverse cardiovascular events reported by investigators are adjudicated by an independent clinical endpoint committee (CEC) in a blinded fashion. The MACE events of special interest are: deaths due to cardiovascular cause, myocardial infarction, hospitalization for unstable angina, hospitalization for heart failure, coronary interventions (such as coronary artery bypass graft [CABG] or percutaneous coronary intervention [PCI]); and cerebrovascular events, including cerebrovascular accident (stroke) and transient ischemic attack (TIA). Deaths with an undetermined cause per CEC will be included in death due to CV cause for analysis purposes.

A listing of patients reporting MACE events, either reported by investigator or identified by the CEC, will be provided. Listing will include treatment, patient identification including the site number, date of event, type of event as reported by the investigator, type of event as adjudicated by the CEC, time from first dose of study drug to the event, time from last dose to the event (if patient has discontinued study drug prior to the event). Only positively adjudicated MACE will be considered as an AESI.

Summaries of positively CEC adjudicated and investigator-reported MACE events will be provided by treatment and event type.

Time-to-first-event analysis of the composite endpoint consisting of positively CEC adjudicated: death due to cardiovascular cause, myocardial infarction, stroke, or hospitalization due to unstable angina (MACE-4) will be conducted.

#### 5.13.2.8. Supraventricular Arrhythmias and Cardiac Conduction Disorders

Adverse event database will be searched using a pre-defined MeDRA terms to identify events consistent with supraventricular arrhythmias and cardiac conduction Disorders. Detailed searching criteria can be found in [Appendix 1](#). Incidence of resulting TEAEs will be summarized by treatment and PT within SMQ and HLT. Treatment-emergent severe/serious supraventricular arrhythmias and cardiac conduction disorders will be considered AESIs.

#### 5.13.2.9. Hypersensitivity Events

Two main analyses are performed for hypersensitivity reactions and related information:

a. **Potential Immediate Hypersensitivity:** Analysis of TEAE occurring from start of study drug administration up to 24 hours after end of study drug administration. For events without the hypersensitivity eCRF, only date (no time) information is collected, the events occurred on the same date as the study drug injection date will be included.

b. **Potential Non-Immediate Hypersensitivity:** Analysis of TEAE occurring more than 24 hours after end of study drug administration, but prior to subsequent study drug administration.

Summaries of all potential hypersensitivity reactions will be generated by PT with decreasing frequency by treatment. The AE database will be searched using predefined SMQs to identify events consistent with hypersensitivity events. Detailed searching criteria for hypersensitivity events can be found in [Appendix 1](#). Severe/serious hypersensitivity events identified by predefined SMQ searches will be considered AESIs.

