7.1. Treatments Administered

Patients will be randomized in a 1:1:1:3 ratio to receive LY3298176 5 mg, LY3298176 10 mg, LY3298176 15 mg, or insulin glargine. LY3298176 will be administered QW as SC injection in patients with T2D who are already treated with a stable dose of at least 1 and no more than 3 oral antihyperglycemic medications: metformin, sodium-glucose co-transporter-2 inhibitors, or sulfonylureas.

Table GPGM.3 shows the randomized treatments for the entire treatment period.

The starting dose of LY3298176 will be 2.5 mg QW for 4 weeks, followed by an increase to 5 mg QW, for the duration of the study low-dose arm. For the 10-mg arm, the starting dose of trizepatide will be 2.5 mg QW for 4 weeks, then the dose will be increased by 2.5 mg every 4 weeks (2.5 to 5 to 7.5 to 10 mg) until the 10-mg dose is reached and maintained for the duration of the study. For the 15-mg arm, the starting dose of LY3298176 will be 2.5 mg QW for 4 weeks, then the dose will be increased by 2.5 mg every 4 weeks (2.5 to 5 to 7.5 to 10 to 12.5 to 15 mg) until the 15-mg dose is reached and maintained for the duration of the study.

The starting dose of insulin glargine will be 10 IU/day at bedtime, titrated to a FBG <100 mg/dL, following a treat-to-target algorithm (Riddle et al. 2003). Patients will titrate the insulin glargine dose in a weekly manner and will make the dose decision with the investigator for the first 8 weeks (phone or clinic visit). For further dose titration, from Week 8 to Week 16, patients will have a phone or clinic visit every other week.

Table GPGM.3. LY3298176 Treatment Regimens

Treatment Group						Treatment Period Interval	
	Weeks 0 to 3	Weeks 4 to 7	Weeks 8 to 11	Weeks 12 to 15	Weeks 16 to 19	Weeks 20 to 104	
15 mg LY3298176	2.5 mg	5 mg	7.5 mg	10 mg	12.5 mg	15 mg	→
10 mg LY3298176	2.5 mg	5 mg	7.5 mg	10 mg →			
5 mg LY3298176	2.5 mg	5 mg →					

Note: All doses will be administered QW using a single-dose prefilled syringe.

The investigator or his or her designee is responsible for the following:

- explaining the correct use of the investigational agent(s) to the patient
- verifying that instructions are followed properly
- maintaining accurate records of investigational product dispensing and collection as well as records of interruptions in study drug administration

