7.2.1.2. Insulin Glargine

Dosing for patients randomized to insulin glargine will start at 10 units once daily. Patients should administer their daily doses at the time of day agreed upon between the patient and the investigator, typically before bedtime. Patients assigned to the insulin glargine treatment arm will be instructed to adjust insulin glargine doses to a target FBG of <100 mg/dL (5.6 mmol/L) based on the median value of the last 3 self-monitored fasting blood glucose (SMBG) values according to the schedule below (Riddle et al. 2003). Insulin glargine dose adjustments should occur once in a week. After Week 8, patients will continue to adjust insulin glargine per the titration algorithm; the insulin glargine dose will be also reviewed and revised, as needed, at subsequent office visits. There will be no central oversight of insulin glargine titration. Add-on

glycemic rescue therapy should be initiated for patients who met prespecified criteria for severe, persistent hyperglycemia, and further titration of glargine cannot control the condition (see [Table GPGM.4](#)).

Table GPGM.4. Titration of Insulin Glargine

Median Fasting Blood Glucose ^a		Adjustment of Insulin Glargine
mg/dL	mmol/L	
≤70	≤3.9	Decrease by 2 to 4 units ^{b,c}
71 to 99	4.0 to 5.5	No adjustment
100 to 119	5.6 to 6.6	Increase by 2 units
120 to 139	6.7 to 7.7	Increase by 4 units
140 to 179	7.8 to 9.9	Increase by 6 units
≥180	≥10.0	Increase by 8 units

Abbreviation: SMBG = self-monitored blood glucose.

^a Based on the last 3 self-monitored fasting blood glucose (SMBG) values.

^b Dose should also be decreased by 2 to 4 units in the following situations:

- If multiple episodes of nonsevere hypoglycemia were recorded during the assessment period at any time during the day; and/or
- If at least 1 episode that met the criteria for severe hypoglycemia (events requiring assistance to administer therapy) or was associated with self-monitored blood glucose (SMBG) value <54 mg/dL (<3.0 mmol/L) was recorded during the assessment period.

^c If only 1 hypoglycemic episode with SMBG value ≥54 mg/dL (≥3.0 mmol/L) and ≤70 mg/dL (≤3.9 mmol/L) was recorded, insulin dose should not be changed.

Source: Riddle et al. 2003.

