There will be 2 estimands of interest in evaluating primary and secondary efficacy objectives. First estimand, the “efficacy” estimand, represents efficacy prior to discontinuation of study drug without confounding effects of rescue therapy for persistent severe hyperglycemia. Analysis relative to “efficacy” estimand will be conducted using EAS. The second estimand, the “treatment-regimen” estimand, represents the efficacy irrespective of adherence to investigational product or introduction of rescue therapy for persistent severe hyperglycemia. Analysis relative to “treatment-regimen” estimand will be conducted using FAS.

Unless specified otherwise, safety analyses will be conducted relative to “treatment-regimen” estimand using the safety analysis set.

End of study participation for a patient will be the earliest of date of death, date of withdrawal from further participation in the study, or date of safety follow-up visit (visit 801). For patients considered to be lost-to-follow-up, end of study participation will be the date of lost-to-follow-up reported by the investigator. Patient data included in database after the last date of study participation (date of death, date of early termination, or date of safety follow-up) will be excluded from statistical analysis. Listing of such data may be provided.

Summary statistics for categorical measures (including categorized continuous measures) will include sample size, frequency, and percentages. Summary statistics for continuous measures will include sample size, mean, standard deviation (SD), median, minimum, and maximum. The summary statistics will be presented by the nominal visit.

Statistical treatment comparisons will only be performed between tirzepatide doses and insulin glargine. Since the trials are not adequately powered to detect differences among tirzepatide doses, comparisons among tirzepatide arms will not be performed unless otherwise specified.

Statistical summaries and results of statistical analysis will be displayed in the following treatment order: 5mg tirzepatide, 10mg tirzepatide, 15mg tirzepatide, and insulin glargine.

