### 5.10.2. Exposure and Compliance to Insulin Glargine Treat-to-Target Algorithm

Summary information of total daily dose of insulin glargine will be reported by visit. Information related to compliance to treat-to-target therapy including reasons for non-compliance will be summarized.

Compliance will be defined as taking at least 75% of the scheduled insulin doses. Compliance will be calculated by taking the number of injections expected minus the total number of injections missed (regardless of the actual dose administered) divided by the total number of injections expected to be administered  $\times 100$ . Treatment compliance will be summarized descriptively using the mITT population.

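### The 24-hour split of hypersensitivity events is not comparable between weekly tirzepatide and once-daily glargine

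*SAP*

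**What the plan says.** SAP 5.13.2.9 sets out two main analyses of hypersensitivity.

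- Immediate: "Analysis of TEAE occurring from start of study drug administration up to 24 hours after end of study drug administration". Events without the hypersensitivity eCRF carry only a date, and for these "the events occurred on the same date as the study drug injection date will be included".
- Non-immediate: events "occurring more than 24 hours after end of study drug administration, but prior to subsequent study drug administration".

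The section then adds: "Summaries of all potential hypersensitivity reactions will be generated by PT with decreasing frequency by treatment". It also makes severe or serious events found by the SMQ search AESIs, whatever their timing.

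Nothing limits the two windows to tirzepatide, and Protocol 9.2.2.2 counts insulin glargine as study drug. The dosing intervals differ by a factor of seven. Protocol 7.1 states "LY3298176 will be administered QW as SC injection in patients with T2D", and Protocol 7.2.1.2 states "Dosing for patients randomized to insulin glargine will start at 10 units once daily".

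SAP 3.4 lists systemic hypersensitivity reactions among the outcomes on which tirzepatide is to be compared with glargine. SAP 5.2 says "Statistical treatment comparisons will only be performed between tirzepatide doses and insulin glargine". SAP 5.13 makes Fisher's exact test the default for categorical safety responses unless something else is specified, and 5.13.2.9 specifies nothing else.

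**The concern.** A fixed 24-hour window after each dose is a small part of a weekly interval and the whole of a daily one. An event with no relation to dosing then falls into a category largely according to how often the arm injects. On glargine almost every such event is immediate by construction, and the non-immediate category is filled only through late or missed doses.

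The two tables would err in opposite directions. The immediate table could hide a tirzepatide excess behind glargine's wider window. The non-immediate table could show a tirzepatide excess that does not exist. For events that are related to dosing, drug effect and dosing interval cannot be separated. The distortion is in the counts, so it is present whether or not a test is run.

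The section does plan a summary of all potential reactions, but it does not say that this summary, and not the two windows it calls main, is the basis for comparing arms.

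**Working it through.** The plan states no figure on this point, so there is none to reproduce.

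**Inputs**
- Dosing interval: 168 h for tirzepatide (Protocol 7.1), 24 h for glargine (Protocol 7.2.1.2).
- Immediate window: 24 h after each dose (SAP 5.13.2.9).
- Compliance floor: 75% of doses in every arm (Protocol 7.6; SAP 5.10.1). For glargine, SAP 5.10.2 says "Compliance will be defined as taking at least 75% of the scheduled insulin doses".
- Planned arm sizes: 313 per tirzepatide dose, 939 glargine (Protocol 5.2).
- Assumed, not in the documents: the same proportion p of patients with an event in both arms, with events spread evenly over on-treatment time. I use p = 1%, 2% and 3.5%.

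**Step 1: share of on-treatment time in the immediate window.** With a fraction m of doses missed at random, the share is (1 − m)/7 for weekly dosing and (1 − m) for daily dosing. Time after the last dose is left out.

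| m | Tirzepatide | Glargine |
|---|---|---|
| 0 | 14.3% | 100% |
| 0.10 | 12.9% | 90% |
| 0.25 | 10.7% | 75% |

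The ratio is 7 to 1 in every row. Varying the time of the daily injection (simulated SD 0.5 to 3 h, no missed doses) lowers the glargine share only to about 99% to 93%. The date-only rule gives the same ratio: one date in seven against every dosed date.

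**Step 2: expected counts, one tirzepatide dose against glargine.**
- Immediate: 313 × p × (1 − m)/7 against 939 × p × (1 − m).
- Non-immediate: 313 × p × [1 − (1 − m)/7] against 939 × p × m.

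Example at p = 2%, m = 0: immediate 313 × 0.02/7 = 0.89 against 939 × 0.02 = 18.78; non-immediate 313 × 0.02 × 6/7 = 5.37 against 0. Counts are rounded and compared with a two-sided Fisher's exact test.

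| p | m | Immediate (p-value) | Non-immediate (p-value) |
|---|---|---|---|
| 3.5% | 0 | 2 vs 33 (0.005) | 9 vs 0 (0.000003) |
| 2% | 0 | 1 vs 19 (0.04) | 5 vs 0 (0.001) |
| 1% | 0 | 0 vs 9 (0.12) | 3 vs 0 (0.016) |
| 3.5% | 0.25 | 1 vs 25 (0.010) | 10 vs 8 (0.005) |
| 2% | 0.25 | 1 vs 14 (0.13) | 6 vs 5 (0.03) |
| 1% | 0.25 | 0 vs 7 (0.20) | 3 vs 2 (0.10) |

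**Step 3: chance of nominal p<0.05 although true rates are equal.** This sums the binomial probabilities over all pairs of counts with Fisher p<0.05, at m = 0.10.

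| p | Immediate | Non-immediate | All events |
|---|---|---|---|
| 1% | 10% | 37% | 3% |
| 2% | 54% | 76% | 4% |
| 3.5% | 87% | 95% | 4% |

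The all-events comparison stays below 5% throughout, so the excess comes from the split and not from the test or the unequal arm sizes.

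**The case against.** The strongest reply is that the comparison that matters is already planned. The objective in SAP 3.4 has no timing split, SAP 5.13.2.9 summarises all potential reactions by treatment, SAP 5.13.1 compares TEAEs at SOC and PT level, and AESIs do not use the 24-hour cut. On this view the remedy mostly relabels an existing table. That limits the reach of the point. It does not remove it, because the section calls the two windows the main analyses and gives the overall summary no such standing.

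Second, applying the split to all arms is a reading: the phrase on treatment sits in the sentence about the overall summary, not in the two definitions. The reading is still the natural one. Study drug includes glargine, and where the SAP means tirzepatide only, as for anti-drug antibodies in 5.13.2.11, it says so.

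Third, no test is named for the windows, safety comparisons carry no multiplicity control (SAP 5.6), and the p-values rest on assumed rates with events unrelated to dosing. This is fair. The p-values are illustrations of size, and they weaken at low rates: at 0.5% with 10% of doses missed, the chances fall to 0.1% (immediate) and 12% (non-immediate). The shares in step 1 need neither a test nor an event rate.

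Fourth, an alert reader would see that a nearly empty non-immediate column for a daily drug is structural, and a cautionary footnote might do. Removing glargine from the split loses some description, and the SAP's revision history says the special safety topics were aligned with a program SAP, so a study-only change may depart from it. These are real but small costs.

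**Conclusion.** The concern holds. As written, the two main hypersensitivity analyses cannot be compared between tirzepatide and glargine, because the immediate window covers about 11% to 14% of on-treatment time in one case and about 75% to 100% in the other. These shares follow from the dosing schedules and the compliance definition, with doses missed at random and time after the last dose left out. The counts and false-signal rates further assume equal event proportions of 1% to 3.5% spread evenly over treatment; they are material at 2% and above and modest at 1%, especially in the immediate table.

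The problem is confined to the split. The all-events summary, the severe/serious AESI count, the comparison among the three weekly arms, and the primary and key secondary analyses are unaffected. It should be corrected, but it does not threaten the trial's main conclusions.

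**What to change.** State in SAP 5.13.2.9 that the comparison between arms uses all treatment-emergent hypersensitivity events from the SMQ search, whatever the time since the last dose, so that the overall summary already planned there becomes the basis for comparison. Keep the immediate and non-immediate categories, but present them descriptively for the tirzepatide arms only, with no comparison to glargine.

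The cost is SAP wording and table shells. The data are already collected. The small loss is glargine's column in the split.

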#### **5.13.2.10. Injection Site Reactions**

Injection site reactions, incidence, and related information reported via “Injection Site Reactions” eCRF will be summarized by treatment. Information to be summarized includes the timing of reaction relative to study drug administration, and characteristics of the injection site reaction: erythema, induration, pain, pruritus, and edema.

Additionally, potential injection site reactions will be searched by pre-defined MedDRA High Level Term (HLT) of injection site reactions and infusion related reactions. Detailed searching criteria for hypersensitivity events can be found in [Appendix 1](#). The PT will be used for summary within each HLT category. Only severe/serious injection site reactions will be considered AESIs.

#### **5.13.2.11. Immunogenicity**

Treatment-emergent anti-drug antibodies (TE ADA) are defined as those with a titer 2-fold (1 dilution) greater than the minimum required dilution if no ADAs were detected at baseline (treatment-induced ADA) or those with a 4-fold (2 dilutions) increase in titer compared to baseline if ADAs were detected at baseline (treatment boosted ADA). A patient is evaluable for TE ADA if the patient has a non-missing baseline ADA result, and at least 1 non-missing postbaseline ADA result.

The frequency and percentage of patients with preexisting ADA, with TE ADA, and with neutralizing TE ADA to tirzepatide will be tabulated by dose, where proportions are relative to the number of patients who are TE ADA evaluable.

A listing may be provided of all immunogenicity assessments for those patients who at any time had TE ADA Present. This includes the tirzepatide concentration from a simultaneous PK sample, and the clinical interpretation result .

Depending on the number of patients with TE ADA, selected efficacy and safety subgroup analyses by TE ADA categories may be performed.

#### **5.13.2.12. Diabetic Retinopathy Complications**

Results of the baseline dilated fundoscopic exam will be summarized by treatment. Any TEAE suspected of worsening retinopathy triggers a follow-up dilated fundoscopic exam. A listing of worsening follow-up dilated fundoscopic exam results will be generated with baseline and postbaseline results.

The cases with repeated fundoscopy during the course of the trial, based on clinical suspicion of worsening retinopathy that have either findings of de novo retinopathy or progression of retinopathy, and severe/serious adverse events from PTs defined in searching criteria in [Appendix 1](#) will be considered as AESIs and summarized.

